## 10.3 Statistical Analysis Plan

10.3.1 We will use the general framework of generalized linear mixed models (GLMM) to test for intervention effects over time. Note that some of our outcomes are binary, some count and some continuous traits, and thus need to be treated differently. The general form of the GLMM will be  $g(\mu_{ij}) = \beta_0 i + \beta_{cov} Covariates_{ij} + \beta_{Time} j + \beta_{Trt} Trt_{Armi} + \beta_{Arm \times Time}$ , where  $\beta$  is the mean response corresponding to subject  $i$  at Time  $j$  (baseline and 4 follow-ups), with its appropriate link function (identity for continuous outcome, logit for binary outcome and natural log for count outcomes);  $Trt = 1$  if the  $i$ -th subject is in the intervention group and 0 if the  $i$ -th subject is in the attention-control group. The interaction coefficients are of interest here, measuring the difference in the rate of change in outcome across the two treatment groups over time. The subject-specific random intercepts are assumed to be normally distributed with a common variance and they account for within-person correlation. We will also explore if we need a subject-specific random-slope corresponding to visit in the above model. Maximum likelihood estimation will be used for fixed effect parameters. Models will be compared according to information criterion like AIC, BIC. For some binary outcomes like HIV testing, we will perform an aggregate analysis after collapsing across the repeated measures using simple logistic regression comparing whether the probability of having tested at least once over the entire FU period is different across treatment groups, after adjusting for baseline values. To ensure robustness, we will also apply an exchangeable working correlation structure to its corresponding generalized estimating equation (GEE) model. We will also conduct exploratory regression analyses to examine city differences in the outcomes. These regressions will be run with group assignment and city in the model, controlling for socio-demographic characteristics.

Interactions between group assignment and city will be tested to explore potential site-specific moderators of treatment effect.

10.3.2 As a secondary analysis, we will build on our GLMM framework to examine whether the intervention effects in the theoretical mediators (e.g., intentions, self-efficacy, perceived barriers) are associated with our outcomes. We will also test whether these relationships vary as a function of YMSM's varying engagement with the intervention (intervention acceptability; use of intervention over time). Interactions between group assignment and these characteristics will test for potential moderators of treatment effect.

10.3.3 For the qualitative interviews of agency directors, initial reading and coding of the transcripts will be reviewed, compared, and refined in team meetings. This systematic process will lead to the creation of a coding structure that includes a hierarchical set of constructs seen in the data. We will analyze several transcripts jointly to establish inter-coder reliability. The team will then code all transcripts using our coding structure and add inductive codes throughout the iterative analysis process. Throughout, we will discuss emerging themes, resolve difficulties or concerns that may arise while coding, and adapt the codebook as necessary. Since we were seeking to gain a multi-level understanding of the structural, organizational, and interpersonal barriers and facilitators of implementing GC, our analysis will utilize a phenomenological framework. Although our analysis will rely primarily on a phenomenological inductive approach, we will also employ aspects of deductive analysis that take into account our guiding conceptual framework. This combination of analytic strategies will allow us to conduct a phenomenological analysis (inductive) that was initially informed by existing research and theory via the conceptual framework (deductive). We will analyze the qualitative data using thematic analysis until we have reached saturation.

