### **Binary outcomes such as HIV testing:**

The percentage of participants who report routine HIV testing over a 12-month period will be compared between the intervention arms (GC and the Control condition). Five assessments will occur at 1 month (visit window  $\pm$  1 month), 3 months ( $\pm$  1 month), 6 months ( $\pm$  1 month), 9 months ( $\pm$  1 month), and 12 months ( $\pm$  1 month). Repeated-measures analyses for HIV testing will be implemented by performing a generalized estimating equations (GEE) analysis via the SAS GENMOD Procedure (version 9.4; SAS Institute, Cary, NC) with an exchangeable correlation structure for the repeated measures within participant (binomial-logit model). The statistical model will include three predictors (intervention arm, time on study and the statistical interaction between intervention arm and time on study). The statistical model will provide estimates of the percentages of participants reporting HIV testing (plus 95% confidence intervals) by intervention arm and time on study. The model-based estimates are unbiased with unbalanced and missing data, so long as the missing data are non-informative (missing completely at random, MCAR). A P value  $\leq 0.05$  will be considered statistically significant for the main effects (intervention and time on study) and for the intervention by time on study interaction effect from the repeated measures analysis. **The statistical test for interaction between time on study and intervention arm will be the primary overall hypothesis test to determine whether HIV testing in the intervention groups changed in significantly different ways during follow-up (i.e., different temporal patterns over time).** If HIV testing rates in the two intervention groups are consistently different or similar (i.e., no statistical interaction) then the main effect test for intervention will be used as the primary test of intervention efficacy. If a significant interaction is detected, then Wald chi-square tests will be used to compare the differences between the model-based HIV testing estimates at each time interval and to compare differences over time within each intervention arm. Specific statistical tests will be done within the framework of the generalized linear model. All statistical tests will be 2-sided and unadjusted for multiple comparisons.

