We will use SurveyGizmo to collect YMSM's data. *At baseline, participants will be logged into the SurveyGizmo assessment by site study staff. For follow-up assessments, participants will receive a unique link which will allow them to complete the surveys in multiple sittings or to resume a survey that has timed out or been closed.* Online surveys allow participants to complete the survey at a convenient location, circumvent barriers (e.g., scheduling, transportation) present in interviewer-administered or phone-based interviews, and decrease social desirability. To maximize completion rates, participants will receive email and/or text reminders that a survey is available. Although we will employ recommended strategies to avoid loss to follow-up, we project a conservative attrition of 20%. In the pilot study, we achieved >80% retention using the approaches proposed here.

Secondary objective:

- **Phase 2a: Enrolling and Training of Mystery Shoppers**  
We will enroll and train 10-15 mystery shoppers per city to conduct the mystery shopper assessments. This approach follows best practices indicating that youth involvement is vital when designing relevant and appropriate HIV interventions for the target population. As study staff, we will work with the ATN site in each city to enroll HIV-negative YMSM (ages 18-24) who are interested in serving as mystery shoppers. We will employ a stratified purposive sampling strategy to ensure age and racial/ethnic diversity across mystery shoppers. Of the 10-15 mystery shoppers in each city, we will attempt to recruit diversity in age and race/ethnicity. Mystery shoppers will be 18 to 24 years old (inclusive).
- **Phase 2b: Site Visits**  
Based on feedback from agency directors in our original study, we will send all agency directors a letter informing them of their site's selection for the study before the mystery shopper visits and contact information to reach the research PIs if they have questions about the procedures. Shoppers will be instructed to report that they do not have income or health insurance and do not possess any proof of identification. In so doing, we will be able to ascertain whether these would be potential barriers to testing at a given location and determine the lowest possible fees that would be charged to a YMSM.
- **Phase 2c: Integration of Scores into GC Console**  

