## **5.3 Randomization Procedures**

For the primary objective, after consent, YMSM are randomized to either the control or intervention condition, stratified by city/SRV site (Intervention, n=240; Control, n=240). Participants will be randomized on a 1:1 basis to either the control or intervention arm.

For the secondary objective, testing sites are randomized by day of the week and time of day. After consent and training, participants will work with study staff to find day and time slots for their site visits.

For the tertiary objective, 10 eligible testing sites in each city will be randomly selected. The site director for those sites will be contacted for an interview.

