## 10.2 Power Estimates

10.2.1 The primary outcomes for the proposed trial are HIV-negative and HIV-unknown YMSM's successful uptake of HIV and STI testing willingness (e.g., HIV/STI testing), and PrEP awareness and willingness. For HIV testing, we define power as correctly identifying the difference in the proportion of YMSM who engage in HIV testing 2 or more times at least 3 months apart in the 12-month follow-up period ("frequent tester") in our treatment arm (GC) vs. our attention-control arm. For STI testing, we define it as receiving at least one STI test during the 12-month follow-up period. For proportions (e.g., HIV testing; PrEP awareness), our sample size calculations are based on a two-sample test of proportions using a two-sided significance level of 0.05. In order to have 80% power to compare GC to the attention-control group, we require at least 400 participants to find an absolute difference of 13% in cross-sectional analyses. Assuming within-person correlation of 0.25, we can detect an 8.8% difference. A less favorable within-person correlation of 0.75 allows us to detect an 11.3% difference.

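### The repeated-measures detectable differences in 10.2 behave as time-averaged arm differences, but 10.3.1 and 2.4 put the arm-by-time interaction first, and no power is stated for it

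*Combined protocol and SAP*

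**What the plan says.** Section 10.2 states that "our sample size calculations are based on a two-sample test of proportions using a two-sided significance level of 0.05", and that for 80% power "we require at least 400 participants to find an absolute difference of 13% in cross-sectional analyses". It then adds two repeated-measures figures: "Assuming within-person correlation of 0.25, we can detect an 8.8% difference", and "A less favorable within-person correlation of 0.75 allows us to detect an 11.3% difference". It does not give the control rate, the number of repeated measures, or whether the contrast is an average over visits or a change.

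Section 10.3.1 specifies a generalized linear mixed model over baseline and four follow-ups with an arm-by-time term, and says: "The interaction coefficients are of interest here, measuring the difference in the rate of change in outcome across the two treatment groups over time".

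Section 2.4 (binary outcomes) describes a GEE model over five follow-up assessments. There the arm-by-time test "will be the primary overall hypothesis test to determine whether HIV testing in the intervention groups changed in significantly different ways during follow-up". If no interaction is found, 2.4 uses the arm main effect as the primary efficacy test, with no adjustment for multiple comparisons. It tests the frequent-tester rate separately, by a pooled two-sided Z-test. The subsection on continuous outcomes repeats the interaction-first rule.

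**The concern.** The power statement and the named test appear to concern different contrasts. Under a common within-person correlation r, the variance of an average over k visits is proportional to (1 + (k − 1)r)/k, so higher correlation hurts. The variance of an arm-by-time contrast is proportional to (1 − r), so higher correlation helps. Section 10.2 treats 0.75 as the worse case, which fits only the average.

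What is at stake is a real, sustained benefit of the size the plan says it can detect. An analyst who follows 10.3.1 literally could report a null interaction for it, in a plan that appears to claim 80% power.

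**Working it through.** **Inputs.** From 10.2: two-sided 0.05, 80% power, 400 participants, differences of 13, 8.8 and 11.3 points, correlations 0.25 and 0.75. From 5.3: "Participants will be randomized on a 1:1 basis to either the control or intervention arm", hence 200 per arm. Visits: baseline plus months 3, 6, 9, 12 (k = 4, taken as the four follow-ups in 10.3.1), or with month 1 added (k = 5, the schedule in 2.4). Assumed, because the documents do not say: equal correlation between all visits, full data on 400, a linear-probability approximation, and the shape of the effect over time.

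**1. The plan's own figures.** The 13-point figure needs exactly 400 participants if the control rate is 25% (assumed). For the other two, the ratio is informative because it hardly depends on the control rate:
- Stated: 11.3/8.8 = 1.28.
- Averaged contrast, √[(1 + 0.75(k − 1))/(1 + 0.25(k − 1))]: 1.29 (k = 3), 1.36 (k = 4), 1.41 (k = 5).
- Change contrast, √(0.25/0.75) = 0.58.

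With k = 3 and a 22% control rate, both assumed, the averaged formula gives required totals of 393 and 408, close to 400. No single control rate fits all three stated figures, and k = 4 or 5 does not fit both repeated-measures figures. The direction is clear; the exact derivation cannot be recovered.

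**2. Standard error.** From the 13-point figure, the standard error of a single-visit difference is 13/(1.960 + 0.842) = 4.64 points.

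**3. Averaged effect over follow-up, 8.8 points, r = 0.25.** SE = 4.64 × √[(1 + 0.25(k − 1))/k].
- k = 4: 4.64 × √(1.75/4) = 3.07; 8.8/3.07 = 2.87; power 82%.
- k = 5: 4.64 × √(2/5) = 2.93; power 85%.

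Using a 25% control rate directly instead gives 84% and 87%.

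**4. Interaction, 8.8 points, r = 0.25, baseline plus four.**
- Slope: SE = 4.64 × √(0.75/90) = 0.424 points per month, where 90 is the sum of squared deviations of the visit months. A constant gap gives slope 6 × 8.8/90 = 0.587, ratio 1.38, power 28%. A gap growing linearly to 8.8 at month 12 gives slope 8.8/12 = 0.733, ratio 1.73, power 41%.
- Joint test, 4 df: noncentrality = Σ(gap − mean gap)²/[(1 − r) × 4.64²]. Constant gap: 3.84, power 31%. Growing gap: 3.00, power 24%.

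**5. Both scenarios together.**

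| Scenario and visits | Averaged over follow-up | Joint, constant gap | Slope, constant gap | Joint, growing gap | Slope, growing gap |
|---|---|---|---|---|---|
| 8.8, r = 0.25, baseline + 4 | 82% | 31% | 28% | 24% | 41% |
| 8.8, r = 0.25, baseline + 5 | 85% | 29% | 19% | 27% | 48% |
| 11.3, r = 0.75, baseline + 4 | 77% | 95% | 87% | 89% | 97% |
| 11.3, r = 0.75, baseline + 5 | 78% | 95% | 67% | 93% | 99% |

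The averaged column assumes a gap that is constant over follow-up. At 0.75 the interaction has more power than the averaged test in every cell except the slope test with month 1 included and a constant gap.

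**6. The sequence in 2.4.** If neither arm has an effect and the two tests are roughly independent, the chance that at least one gives p ≤ 0.05 is 1 − 0.95² = 9.75%.

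**7. Averaging over all visits.** If baseline is included in the average in the 10.3.1 model, a constant 8.8-point gap becomes 8.8 × 4/5 = 7.04, with SE 4.64 × √(2/5) = 2.93, and power 67%. The average therefore has to be over follow-up only.

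**The case against.** The strongest reply is that the plan already handles a sustained effect. Section 2.4 moves to the arm main effect when the arms differ consistently, and that test has about 82% to 87% power at 8.8%. With only follow-up visits in the model, a constant gap contains no interaction at all, so the 5% rejection rate there is the size of the test and not a defect. Section 10.1.1 also plans regressions with group assignment alone. Section 10.3.1 adds an aggregate logistic comparison of ever having tested. The frequent-tester outcome, which is how HIV testing is defined for the trial, is compared by a pooled Z-test that matches the 13% calculation. STI testing is also defined as a single 12-month proportion.

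All of this stands, and it limits the point. A reader might infer that the trial as a whole has about 30% power, or that the interaction is underpowered in general. The documents support neither: the fallback and the Z-test are in the plan, no effect shape is stated, and at 0.75 and 11.3% the interaction mostly does better than the average.

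Three things are left unanswered. The longitudinal model in 10.3.1 has no fallback to a main effect. The 2.4 sequence gives two unadjusted chances at 0.05. And nowhere is power stated for the test that both sections put first.

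**Conclusion.** The mismatch is real but bounded. The 8.8% and 11.3% figures behave as time-averaged differences, while 10.3.1 and 2.4 give priority to arm-by-time. At 8.8% and correlation 0.25, with baseline in the model, the interaction has roughly 20% to 45% power. At 11.3% and 0.75 the order stated in 10.2 is mostly reversed. That 10.2 used an averaged contrast is inferred from the direction and ratio of its figures, since the plan does not say so.

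The power values rest on equal correlations, 200 per arm with full data and the two effect shapes shown. Other shapes and visit sets give results from 5% to over 90%, so no single percentage should be attached to the interaction until the sponsor states the time pattern.

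**What to change.** In 10.3.1 and in the bold sentence of 2.4, name the one-degree-of-freedom arm effect averaged over the follow-up surveys as the repeated-measures efficacy test, and say that the 8.8% and 11.3% figures in 10.2 refer to it. Make arm-by-time a secondary description of timing. This also removes the unadjusted interaction-then-main-effect sequence. Align the parallel sentence for continuous outcomes. The Z-test for frequent testers is unaffected. In 10.2, state the control rate and the number of visits used.

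If the sponsor prefers to keep the interaction as the primary test, remove the 8.8% and 11.3% claims for it. Recompute its detectable difference with the control rate, the visits and the assumed time pattern stated. The percentages above are illustrations and should not be copied into the plan as replacements.

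The first option changes wording only, with no extra participants or data. Its small downside is that an effect confined to the late surveys is diluted in the average, though the secondary interaction can still show it.

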### 3.0 STUDY DESIGN

#### 3.1 Study Phases

In this four-year study, we will enroll 480 self-reported HIV-negative or sero-status unaware, sexually active YMSM (ages 15-24) across three sites and randomize them into the GC intervention condition or to an attention-control condition. Primary outcomes will include (1) use of HIV prevention services (HIV testing, STI testing) and PrEP awareness and willingness. As secondary outcomes, we will assess PrEP use, sexual risk behaviors, and the linkage and retention in care among newly diagnosed HIV+ cases. We will also examine changes in GC's theorized mechanisms of change, including YMSM's attitudes, norms, self-efficacy, and behavioral intentions to adopt HIV prevention services.

Control condition: Participants randomized to the control condition will have access to the site locator portion of the Get Connected website, which includes information on HIV prevention services. While the provision of a test locator is a form (albeit weak) of an intervention, we felt that withholding referrals to testing and care services would be unethical given YMSM's vulnerability to HIV and STIs. Furthermore, given the availability of search engines to locate HIV/STI testing sites, the test locator condition may be considered usual care. Nevertheless, by providing the testing site locator only, we will be able to test the effect of the GC intervention condition (i.e., user-tailored content focused on HIV/STI testing and PrEP referral and the linkage to high-quality agencies) against the usual care control condition.

Intervention condition: Using a consensus approach to conceptualize health behavior change, the model guiding GC synthesizes The Integrated Behavioral Model and Self-Determination Theory as the theoretical underpinnings of our intervention. These theories emphasize social cognitive factors that impact behavior change and have informed HIV interventions. Consistent with these theories, GC content follows motivational interviewing (MI) principles by focusing on resolving ambivalence about HIV prevention behaviors, increasing self-efficacy for change, and enhancing motivation moving toward action. The intervention was developed by customizing content based on YMSM's psychosocial and sexual

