## 4.0 ELIGIBILITY AND SCREENING

### 4.1 Primary Objective (RCT): Inclusion Criteria

- *Assigned male sex at birth and currently identifies as male*

- *Aged 15 to 24 years (inclusive) at time of screening*
- *Self-report as HIV-negative or sero-status unaware*
- *Speak and read English*
- *Not be on PrEP at time of enrollment*
- *Report having consensual anal sex with a male partner in the prior 6 months and/or report having not received HIV testing in prior 6 months*
- *Reside in Philadelphia, Houston, or Atlanta*
- *Access to internet*

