### 6.1.2 On-study Evaluations/Measures

- *HIV Testing:* Follow-up surveys will repeat the HIV testing questions in each follow-up survey. The HIV testing outcome will be: the proportion of MSM tested for HIV two or more times at least 3 months apart in the 12-month follow-up period (“frequent tester”). As an additional analysis, we will also examine the proportions of participants who receive one HIV test.
  - Among self-reported newly diagnosed HIV+ cases, we will measure their linkage and engagement with appropriate medical care after initial diagnosis using criteria employed in prior ATN protocols with youth. We will define linkage as an HIV-related medical visit within 45 days of referral, and engagement as a second HIV-related medical visit within 16 weeks of initial visit. Onset of ART initiation, self-reported adherence to ART, and viral suppression are exploratory indicators, as we recognize that our follow-up period may not be a sufficient amount of time to see these changes.
- *STI Testing:* The STI testing outcome is defined as the proportion of YMSM tested for STIs at least once in the 12-month follow-up period. We will ask participants what STIs they have been tested for, the anatomic sites where they were tested, the date of their most recent STI test (if known), and whether a medical provider had diagnosed them with an STI. In the follow-up surveys, we will ask participants whether they had been tested for STIs in the past 3 months (for the 1-month follow-up survey, we ask about the past 30 days). If STI testing is reported, we will ask participants to indicate what tests they received, and whether they were diagnosed with an STI by a medical provider.
- *PrEP Use:* At each follow-up assessment, PrEP-eligible HIV-negative YMSM (per CDC guidelines) will be asked whether they have begun using PrEP. We will also ascertain if a provider recommended PrEP and/or were offered a prescription for PrEP.
 

*Site Evaluations:* Across both trial arms, YMSM who report testing in the prior 3 months will complete self-evaluation forms of their testing experiences to assess comfort, quality, and concerns after visiting a site for HIV/STI testing and PrEP prevention services. The assessment form is the same form used by the mystery shoppers. We will use these data to update the WebApp and to send aggregate data of YMSM's satisfaction with services to agencies biannually.

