## **10.0 STATISTICAL/ANALYTIC CONSIDERATIONS**

### **10.1 Introduction**

10.1.1 We will test the efficacy of GC in increasing HIV-negative or HIV-unknown YMSM's successful uptake of HIV and STI testing (e.g., routine HIV/STI testing) and increase in PrEP awareness and willingness, as compared to the attention-control condition over a 12-month period. Descriptive statistics of the psychosocial and demographic characteristics of the participants will be described for all and by intervention group. These will be compared between treatment groups using t-tests or Wilcoxon rank sum tests for continuous variables and chi-square tests for categorical variables. To test for intervention efficacy, we will conduct primary

analyses of our primary outcomes using regression analyses to compare our treatment group to the control using the appropriate link function (identity for continuous outcome, logit for binary outcome, and natural log for count outcomes). The regression will be run with group assignment only in the model, as well as, controlling for participants' socio-demographic characteristics, ATOD and psychological distress, and intervention-related process data (e.g., frequency of use, acceptability). Interactions between group assignment and these characteristics will be tested to explore potential moderators of treatment effect. We will repeat these analyses for the secondary outcomes (e.g., theoretical mediators)).

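### For PrEP use, Section 10.3.1 targets arm-by-time change from a baseline that is zero by eligibility; the plan should name an arm effect over follow-up as the test

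*Combined protocol and SAP*

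**What the plan says.** Section 3.1 makes PrEP use a secondary outcome: "As secondary outcomes, we will assess PrEP use, sexual risk behaviors". Section 4.1 requires that participants "Not be on PrEP at time of enrollment", and Section 4.2 excludes current users. Section 6.1.2 measures use at each follow-up, when PrEP-eligible HIV-negative men "will be asked whether they have begun using PrEP". The PrEP items that Section 6.1.1 lists for the baseline survey are awareness and willingness, not own use.

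Section 10.3.1 gives one general mixed model for the trial's outcomes. Its time points are "baseline and 4 follow-ups" and its links are "identity for continuous outcome, logit for binary outcome and natural log for count outcomes". Correlation is handled within person: "The subject-specific random intercepts are assumed to be normally distributed with a common variance". On what is to be tested it says: "The interaction coefficients are of interest here, measuring the difference in the rate of change in outcome across the two treatment groups over time".

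Two other sections bear on the point. Section 2.4 uses the arm main effect when there is no interaction, but among binary outcomes it extends that plan only to the other primary ones. Section 10.1.1 describes a regression of outcome on group assignment, without and then with covariates, and adds: "We will repeat these analyses for the secondary outcomes".

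**The concern.** An arm-by-time coefficient measured from baseline makes sense when the baseline value can vary. For PrEP use it cannot: everyone enters at zero. Any difference between arms during follow-up is already the treatment effect, and a term for differential change from baseline adds nothing.

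The interaction then has one of two defects. It is undefined if baseline is a separate category filled with zeros. Otherwise it asks whether the arms drift further apart during follow-up, which is a different question from whether the intervention raises PrEP use. An intervention that raised use from month 1 and held the gain could be reported as showing no difference in change. Such a pattern is plausible, because participants open the WebApp straight after the baseline survey (Section 5.1).

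**Working it through.** **Inputs from the documents.** PrEP use is 0% in both arms at entry (Sections 4.1, 4.2). Allocation is 1:1 (Section 5.3). The retained sample is about 400 (Section 3.3), so 200 per arm. The test is two-sided at 0.05 and the link is logit.

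**The plan's own figure.** Section 10.2 states no figure for PrEP use. Its general figure, 400 participants for a 13-point difference at 80% power, reproduces at 25% against 38% (power 80.1%). The control rate there is not stated.

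**Assumed, because the documents give no PrEP-use rates.** Control use is 3%, 5%, 7%, 8.5% and 10% at months 1 to 12, with a constant odds ratio (OR) of 2.0 to 2.5. Other rates are shown below.

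**Step 1: categorical time with baseline zeros.** The interaction at visit j is

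(logit p1j − logit p10) − (logit p0j − logit p00),

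where the first subscript is arm (1 = intervention) and the second is visit (0 = baseline). With p10 = p00 = 0, both baseline logits are minus infinity and the difference is undefined. The data fix only the sum of the arm coefficient and each interaction. In one simulated trial (10% against 20%), two solutions had the same log-likelihood, −548.2069:

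| Arm coefficient | Interactions | Sums |
|---|---|---|
| −1.26 | 3.10, 2.23, 3.01, 2.57 | 1.84, 0.97, 1.75, 1.31 |
| −6.26 | 8.10, 7.23, 8.01, 7.57 | 1.84, 0.97, 1.75, 1.31 |

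An exchangeable GEE, the robustness check in Section 10.3.1, returned no standard errors for the arm and interaction terms in a data set simulated at the same rates.

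**Step 2: follow-up records only.** The contrasts are now finite; the median largest interaction standard error was about 0.5-0.6. Under a constant odds ratio, however, each interaction is log OR − log OR = 0, so power for it equals alpha.

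**Step 3: linear time.** A constant effect is carried mainly by the arm coefficient, not the slope difference. Simulated rejection rates, 200 per arm:

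| Scenario | Linear arm-by-time, with baseline | Arm effect, follow-ups only |
|---|---|---|
| OR 2.0, 2.25, 2.5; robust logit, 600 runs | 6%, 8%, 7% | 62%, 77%, 90% |
| Same ORs; random-intercept GLMM, 120 runs | 4%, 9%, 11% | 76%, 93%, 93% |
| Flat, parallel-rising or narrowing effects (e.g. 2% v 8%, 5% v 12%, 10% v 20%); GLMM, four follow-ups | 1-9% | 94-100% |
| Diverging effects (5% flat v 5 to 20%; 10% flat v 10 to 22%); GLMM, four follow-ups | 55-91% | 80-100% |

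A further run at the assumed rates gave 5-7% for linear arm-by-time with or without a baseline row. For a gradual effect (3.5% rising to 20%), arm-by-time gave 38% against 80% for a person-level comparison. With no true effect, the follow-up arm test rejected in 5-8% of runs.

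**Step 4: hand check of a person-level comparison at month 12.** At OR 2.0, 10% becomes 0.2222/1.2222 = 18.2%. The pooled standard error is √(2 × 0.1409 × 0.8591/200) = 0.0348 and the unpooled one is 0.0346. Then z = (0.0818 − 1.96 × 0.0348)/0.0346 = 0.39, or about 65% power; simulation gave 68%. At OR 2.5 (21.7%), z = (0.1174 − 1.96 × 0.0365)/0.0361 = 1.27, or about 90%; simulation gave 91%.

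**The case against.** The strongest reply is that Section 10.1.1, not 10.3.1, is the text that expressly reaches secondary outcomes, and what it repeats is a group-only regression with no time term. That stands. Simulated at the assumed rates, the group-only test had 73% power at OR 2.0 and 95% at OR 2.5, and a baseline row of zeros left its rejection rates unchanged. A reader might infer that PrEP use has no workable planned analysis; the documents do not support that. Still, Section 10.1.1 does not say how the follow-ups are combined, and Section 10.3.1 names a different target. The plan therefore holds two tests of very different power and no rule for which one decides.

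A second reply is that no baseline PrEP-use item is described, so the inestimable contrasts arise only if someone fills in the zeros that eligibility guarantees. That also stands: failure to fit is conditional, not certain. Leaving baseline out cures it but keeps the interaction as the target (Step 2).

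Third, a reader might infer that any real effect would be missed. That is too strong. Content is retailored after each survey (Section 5.4.1), so a growing effect is plausible, and the linear interaction would often detect it.

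Finally, Section 10.3.1 is worded as a general framework and plans a collapsed analysis for some binary outcomes. PrEP use is not named there, and the baseline adjustment it specifies would be a constant or absent for this outcome.

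**Conclusion.** The point holds for the interaction target in Section 10.3.1 as applied to PrEP use. For an early, sustained effect, the arm-by-time test has power near alpha (about 5-10%) where an arm effect has roughly 60-95% at odds ratios of 2.0 to 2.5. For growing effects it keeps about 38-91%. With categorical time and a filled-in baseline, the contrasts against baseline do not exist.

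The figures rest on assumed use rates and 200 per arm. Section 6.1.2 asks only PrEP-eligible HIV-negative men, a subset of unstated size, so absolute power would be lower if that subset is smaller; the contrast between the two tests is the finding. One secondary outcome is affected. Nothing here bears on the primary HIV-testing analysis, and the group-only comparison in Section 10.1.1 remains valid.

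**What to change.** Add one or two sentences to Section 10.3.1. For PrEP use, no baseline record enters the response and baseline use is not an adjuster. The efficacy test is one named arm effect, either:

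- the arm effect over the follow-up surveys, from the longitudinal model; or
- the arm effect in a person-level logistic regression of having started PrEP by month 12 on arm and city.

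These are different estimands (use averaged over visits, and initiation by a fixed time), so the sponsor should choose one. Arm-by-time results for PrEP use then become descriptive.

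The cost is the added text; no new data or visits are needed. The one downside is that the test no longer targets differences in the pattern over time.
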